## **3. Time on eslicarbazepine acetate monotherapy**

Time on eslicarbazepine acetate monotherapy during Post1-Year Open-Label Period will be calculated from the date of the first eslicarbazepine acetate monotherapy dose in protocol 093-045 or 093-046(Visit 6/Week 8) to the last known dose of eslicarbazepine acetate monotherapy during Post-1-Year Open- Label Period as follows;

- For a subject who added a non-rescue AED during Post-1-Year Open-Label Period, Time on Monotherapy during Post 1-Year Open-Label Period is calculated as the date of start a non-rescue AED during Post-1-Year Open-Label Period minus the date of the first monotherapy dose in protocol 093-045 or 093-046.
- For a subject who completed the Post-1-Year Open-Label Period, and did not add any non-rescue AED since the date of the first monotherapy dose in protocol 093-045 or 093-046, Time on Monotherapy during Post-1-Year Open-Label Period is calculated as the date of the last known dose during Post-1-Year Open-Label Period, minus the date of the first monotherapy dose in protocol 093-045 or 093-046, plus 1.
- For a subject who did not complete the Post-1Year Open-Label Period and did not add any non-rescue AED since the date of the first monotherapy dose in protocol 093-045 or 093-046, Time on Monotherapy during Post- 1-Year Open-Label Period is calculated as the date of the last known dose before the withdrawal during Post- 1-Year Open-Label Period, minus the date of the first monotherapy dose in protocol 093-045 or 093-046, plus 1.

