**4. Responder rate**

Responder is defined as having a ≥50% reduction in SSF from baseline.

The proportion will be calculated as the number of responders divided by the total number of subjects in the ITT population entering the period of interest.

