## **4. Treatment retention time**

If a subject’s reason for withdrawal from Post-1-Year Open-Label Period included: withdrawal of consent, lost to follow-up, physician decision or other, then it will be assumed the subject terminated due to lack of efficacy. For subjects that discontinue due to adverse event or lack of efficacy, the treatment retention time during Post-1-Year Open-Label Period will be calculated as the date of last known dose during Post-1-Year Open-Label Period minus the date of the first dose of eslicarbazepine acetate monotherapy in protocol 093-045 or 093-046 (Visit 6/Week 8), plus 1. The time may include taking eslicarbazepine acetate concomitantly with other AEDs.

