## **7. Statistical Analysis**

### **7.1 Analysis Populations**

The intent-to-treat (ITT) population will consist of all subjects who have taken any open-label study medication. The ITT population will be used for all safety and all efficacy analyses.

The per-protocol (PP) population will consist of all subjects in the ITT population who did not have any important protocol deviations. The per-protocol population will be used in an additional analysis of the efficacy endpoints and subject demographics and baseline characteristics.

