### **Time on eslicarbazepine acetate monotherapy**

Kaplan Meier methods will be used to estimate the median time (and 95% CI) on eslicarbazepine acetate monotherapy for both 1-Year Open-Label Period and Post-1-Year Open-Label Period.

For the 1-Year Open-Label Period, time on monotherapy as defined in Section 5.2.2 will be used for analysis. Subjects who were still taking only eslicarbazepine acetate as monotherapy at the end of the 1-Year Open-Label Period of study will be censored at the last dose of the 1-Year Open-Label Period. Subjects who withdrew during the 1-Year Open-Label Period will also be censored at the time of the last known dose before the withdrawal. Subject who added a non-rescue AED will be an event on the date of the start AED during 1-Year Open-Label Period.

For the Post-1-Year Open-Label Period, time on monotherapy as defined in Section 5.2.3 will be used for analysis. Subjects who were still taking only eslicarbazepine acetate as monotherapy at the end of the Post-1-Year Open-Label Period will be censored at the last dose of the Post-1-Year Open-Label Period. Subjects who withdrew during the Post-1-Year Open-Label Period will also be censored at the time of the last known dose before the withdrawal. Subject who added a non-rescue AED will be an event on the date of the start AED during Post-1-Year Open-Label Period.

Subjects who never started the monotherapy treatment period in protocol 093-045 or 093-046 will not be included in this analysis. Change in dosage levels from protocol 093-045 or 093-046, dosage changes during protocol 093-050, and the time gap between the parent studies and the extension study will be ignored.

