**Treatment retention**

Kaplan Meier methods will be used to estimate the median retention time (and 95% CI) on eslicarbazepine acetate for subjects who discontinued early due to adverse event(s) or lack of efficacy for both 1-Year Open-Label Period and Post-1-Year Open-Label Period.

For 1-Year Open-Label Period, subjects who discontinued the study not due to those reasons (i.e. protocol deviation) as defined in Section 5.2.2 will be censored at the date of the last known dose during 1-Year Open-Label Period. Subjects who were still taking eslicarbazepine acetate at the end of the 1-Year Open-Label Period of study will be censored at the last dose of the 1-Year Open-Label Period.

For Post-1-Year Open-Label Period, subjects who discontinued the study not due to those reasons (i.e. protocol deviation, study drug became available in subject's locale, and sponsor terminates clinical study) as defined in Section 5.2.3 will be censored at the date of the last known dose during Post-1-Year Open-Label Period. Subjects who were still taking eslicarbazepine acetate at the end of the Post-1-Year Open-Label Period of study will be censored at the last dose of the Post-1-Year Open-Label Period.

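### The Post-1-Year time-on-monotherapy and retention curves start at parent-study Week 8, so each time carries about a year in which no event can be recorded

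*SAP*

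**What the plan says.** SAP 5.2.3 item 3 says that time on monotherapy "during Post1-Year Open-Label Period will be calculated from the date of the first eslicarbazepine acetate monotherapy dose in protocol 093-045" or 093-046, at Visit 6/Week 8. Three bullets then assign values: to a subject who starts a non-rescue AED in the Post-1-Year period, to one who completes the period without such an AED, and to one who withdraws in the period without such an AED. Item 4 gives retention as the "date of last known dose during Post-1-Year Open-Label Period minus the date of the first dose of eslicarbazepine acetate monotherapy" in the parent study, plus one day.

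SAP 7.6 carries this into the analysis: "For the Post-1-Year Open-Label Period, time on monotherapy as defined in Section 5.2.3 will be used for analysis". The events and censoring it describes for this curve all fall within the period. Retention is handled the same way. The sentence that begins "For Post-1-Year Open-Label Period, subjects who discontinued the study not due to those reasons" censors those subjects at their last dose in the period. For monotherapy, 7.6 excludes anyone who never began parent-study monotherapy and adds that "the time gap between the parent studies and the extension study will be ignored". Delayed entry is not mentioned.

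On population, 7.1 states: "The ITT population will be used for all safety and all efficacy analyses". For the responder rate, 5.2.2 item 4 narrows the denominator to "the total number of subjects in the ITT population entering the period of interest". No such limit is given for these two curves.

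The first bullet of item 3 opens "For a subject who added a non-rescue AED during Post-1-Year Open-Label Period" and sets no condition on earlier AED additions. The other two bullets require that none has been added since monotherapy began.

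**The concern.** A reader of a Post-1-Year median will take it as how long monotherapy or treatment lasted after Visit 7. Under these definitions it is time since Week 8 of a different study, in subjects who had to get through year 1 to be counted. The time they had to survive is credited to the result.

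Maintenance of effect in the Post-1-Year period is a secondary objective (SAP 2.2). The seizure diary stops at Visit 7 (SAP 5.2.1), so no seizure-frequency endpoint covers the period. These two curves are its only time-to-event estimates, and both would make durability after year 1 look longer than it was.

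**Working it through.** **Inputs**
- Parent treatment phase: 18 weeks (SAP 3.1). Monotherapy starts at Week 8 (5.2.3).
- Parent monotherapy: 18 − 8 = 10 weeks = 70 days. This reproduces the 10 weeks stated in SAP 6.5. Subjects who discontinued or exited the parent study may also enter (3.1), so the range is 0 to 70 days.
- Year 1 of 093-050: taken as 365 days. The documents give no visit windows; 360 to 366 days shifts everything below by at most 5 days.
- Event rates: none are given, so the rates below are assumptions.

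**Who contributes.** Take a subject who withdrew in year 1, one who finished year 1 and did not continue, and one who added an AED only in year 1. None fits a bullet of item 3. For retention, item 4 needs a last dose in the Post-1-Year period, so the first two have no value there either. Only entrants have times.

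**Lead-in.** 365 + 0 = 365 days to 365 + 70 = 435 days, plus any gap between studies that stays in the date difference. No event can be recorded in this block. If half of the entrants failed within 30 days of Visit 7, the median would still read 365 + 30 = 395 to 435 + 30 = 465 days.

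**Illustration with a constant hazard h per year.** Median from Visit 7 = (ln 2 / h) × 365.25. As written, add 365 to 435.

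| h per year | From Visit 7 (days) | As written (days) |
|---|---|---|
| 0.25 | 1,013 | 1,378–1,448 |
| 0.5 | 506 | 871–941 |
| 1.0 | 253 | 618–688 |
| 2.0 | 127 | 492–562 |

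At 1.0 per year the reported figure is 618/253 = 2.44 to 688/253 = 2.72 times the Visit 7 median.

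**Simulation check.** This assumed exponential times, 70% of subjects with the full 70 parent days and the rest spread over 1 to 70, no gap, and entrants event-free at Visit 7. For true medians of 365, 730 and 1,460 days, the origin as written gave 795, 1,152 and 1,895 days. Starting at Visit 7 gave 371, 730 and 1,465. The differences are 424, 422 and 430 days, and the shortest recorded time was 371 to 379 days. Analysing the whole cohort with year-1 events counted and delayed entry at Visit 1 gave 371, 693 and 1,457, so the built-in block disappears.

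**First bullet of item 3.** A subject who added one AED in year 1 and another after Visit 7 meets this bullet and is timed to the second addition. The lead sentence of the same item measures to the last monotherapy dose in the period, and this subject had none. Such a subject can enter only as an event, because the other two bullets exclude prior adders. The limit of two additional AEDs (SAP 3.1) restricts how many can do this. The size of the effect depends on the share of year-1 adders and their later rate of adding, and neither can be derived from the documents.

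**The case against.** The best defence is that the origin is openly stated and is the same in 5.2.2 and 5.2.3, so the authors may have meant cumulative time since monotherapy began; relabelling would then be enough. The first part is fair. The second is not: a cumulative curve has to count year-1 events, and 5.2.3 gives those subjects no time.

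A reader might also infer more than the documents support:
- *That no population is named.* ITT is named in 7.1 and 7.6, and one exclusion is stated for monotherapy. What is missing is the subset at risk at Visit 7. The contrast with the responder rate is only suggestive, since the neighbouring Post-1-Year completion rate uses plain ITT.
- *That the lead-in is guaranteed event-free for both endpoints.* That holds for retention, where entry implies no earlier withdrawal. For monotherapy, the gap in the first bullet breaks it.
- *That nothing else describes the period over time.* PGI is summarised every three months (5.2.3, 7.6), and exposure is summarised in coarse duration categories from the first 093-050 dose (7.5).
- *That the entrants-only and cumulative readings always differ by 365 days.* That needs a constant hazard. With Weibull times, no parent lead-in and cumulative medians of 253 to 1,013 days, the difference is 479 to 588 days at shape 0.8 and 201 to 276 at shape 1.3.

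The medians may also not be reached. And no test or decision rule rests on them: safety is the primary objective (2.1) and sample size has no statistical basis (3.3).

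**Conclusion.** The point stands and should be fixed. Followed as written, the SAP produces Post-1-Year medians that, if reached, include about 365 to 435 days in which no event could be recorded, before any gap between studies. This rests on the entrants-only reading, which the definitions imply but do not state, and on a 365-day first year. The tabulated medians also assume a constant hazard and are illustrative only. Under the cumulative reading the block is not built in, but the period label is then wrong and the rules for year-1 events are missing, so the text must change either way. The missing condition in the first bullet is a separate, smaller defect of unknown size. The consequence is a misleading descriptive estimate of durability, not an invalid test.

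**What to change.** In SAP 5.2.3 items 3 and 4 and in 7.6:
- Start both Post-1-Year clocks at Visit 7, in subjects who entered the period. For monotherapy, limit this to those with no non-rescue AED added since their first monotherapy dose, and add that condition to the first bullet of item 3.
- If time since first monotherapy dose is also wanted, present one cumulative curve that counts year-1 events and label it cumulative. State the assumption made about entry from the parent studies. Subjects who discontinued or exited those studies may enter, so time of entry may be related to outcome, and a delayed-entry analysis that assumes otherwise is open to doubt.
- For any retention curve that keeps the parent-study origin, state that subjects with no parent monotherapy dose are excluded, or give their start date. For the Visit 7 curve, say whether they are included.

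The cost is SAP wording and two re-run Kaplan-Meier analyses, using dates already needed for the current definitions. Moving the origin makes the reported medians about 365 to 435 days shorter. Limiting the monotherapy analysis to those still on monotherapy at Visit 7 may lengthen that median.

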Subjects who enter the present study will receive a starting dose of 1600 mg QD of eslicarbazepine acetate, orally for 1 week at the start of the 1-Year Open-Label Period. The starting dose for subjects who had a dose reduction during participation in studies 093-045 or 093-046 will be 1200 mg and not 1600 mg. At the end of this 1-week period, subjects will be allowed to continue at this dose or at the discretion of the Investigator, increase, or decrease dose as necessary for efficacy or tolerability reasons. There is no limit on the number of dose increments or reductions during the study, however, all dose increases or reductions should occur in steps of 400 mg and a minimum of 1 week must pass between one dose change and the next. Dose reductions of more than 400 mg are allowed at the discretion of the Investigator for a documented safety reason. The maximum allowed dose of eslicarbazepine acetate is 2400 mg QD and the minimum allowed dose is 800 mg QD in this study. Subjects who continue into the Post-1-Year Open-Label Period part of the study will continue to receive the same dose of study drug that they received at Visit 7 (end of 1-Year Open-Label Period of treatment). The same dosing rules as in the 1-Year Open-Label Period part of the study are applicable in the Post-1-Year Open-Label Period part. Subjects with a clinically significant increase in seizure frequency, duration, or severity, who have not responded to or did not tolerate an increase in dose of study drug, may be started on an additional antiepileptic drug (AED) during both the 1-Year Open-Label Period and Post-1-Year Open-Label Period parts of the study. A maximum of two additional AEDs to control seizures will be allowed, however oxcarbazepine will not be allowed. If, after the addition of the second additional AED, the subject experiences an adverse event, the dose of eslicarbazepine acetate should be reduced before changing the dose of the concomitant AED. In addition, for subjects with a vagal nerve stimulator (VNS), the device setting may be changed as needed.

Subjects who require doses outside of the 800 mg QD to 2400 mg QD range or more than 2 additional AEDs during the 1-Year Open-Label Period or Post-1-Year Open-Label Period parts of the study will be discontinued from study participation.

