### 5.2.2. 1-Year Open-Label Period Efficacy Endpoints

#### 1. Time on eslicarbazepine acetate monotherapy

Time on eslicarbazepine acetate monotherapy during 1-Year Open-Label Period will be calculated from the date of the first eslicarbazepine acetate monotherapy dose in protocol 093-045 or 093-046 (Visit 6/Week 8) to the last known dose of eslicarbazepine acetate monotherapy during 1-Year Open-Label Period as follows;

- a. For a subject who added a non-rescue AED during 1-Year Open-Label Period, Time on Monotherapy during 1-Year Open-Label Period is calculated as the date of start a non-rescue AED during 1 Year Open-Label Period minus the date of the first monotherapy dose in protocol 093-045 or 093-046.
- b. For a subject who completed the 1-Year Open-Label Period, and did not add any non-rescue AED since the date of the first monotherapy dose in protocol 093-045 or 093-046, Time on Monotherapy during 1-Year Open-Label Period is calculated as the date of the last known dose during 1-Year Open-Label Period, minus the date of the first monotherapy dose in protocol 093-045 or 093-046, plus 1.
- c. For a subject who did not complete the 1-Year Open-Label Period, and did not add any non-rescue AED since the date of the first monotherapy dose in protocol 093-045 or 093-046, Time on Monotherapy during 1-Year Open-

Label Period is calculated as the date of the known dose before the withdrawal during 1-Year Open-Label Period, minus the date of the first monotherapy dose in protocol 093-045 or 093-046, plus 1.

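### The Post-1-Year time-on-monotherapy event is any AED started in that period, not the first AED added since monotherapy began, so a subject who adds AEDs in both periods is timed to the second one

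*SAP*

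**What the plan says.** **Origin.** SAP Sections 5.2.2 item 1 and 5.2.3 item 3 both start the clock at the first monotherapy dose in study 093-045 or 093-046. The two period analyses therefore measure from the same day.

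**Post-1-Year derivation (Section 5.2.3 item 3).** The lead-in runs the interval "to the last known dose of eslicarbazepine acetate monotherapy during Post-1-Year Open- Label Period as follows". Three bullets follow. In the event bullet, the time "is calculated as the date of start a non-rescue AED during Post-1-Year Open-Label Period minus the date of the first monotherapy dose". The other two cover completers and non-completers and run to the last known dose. Both apply only to a subject who "did not add any non-rescue AED since the date of the first monotherapy dose in protocol 093-045 or 093-046". The event bullet has no such condition.

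**Post-1-Year analysis (Section 7.6).** The text first adopts the Section 5.2.3 definition. It then censors subjects who are still on eslicarbazepine acetate alone at the end of the period, and censors withdrawals at their last dose before withdrawal. For events it says: "Subject who added a non-rescue AED will be an event on the date of the start AED during Post-1-Year Open-Label Period". The only subjects left out are those who never started the parent-study monotherapy phase.

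**1-Year derivation (Section 5.2.2 item 1, rule a).** The wording is parallel: the time is "calculated as the date of start a non-rescue AED during 1 Year Open-Label Period minus the date of the first monotherapy dose".

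**Added AEDs (Section 3.1).** Additions may be made in either period: "A maximum of two additional AEDs to control seizures will be allowed".

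**The concern.** Monotherapy ends when the first non-rescue AED is added. The Post-1-Year event rule instead looks only for an AED started inside that period, while still counting time from the parent study. If a first AED came in the 1-Year Period and a second came later, the rule passes over the date on which monotherapy ended and uses a later one.

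At stake is the Post-1-Year Kaplan-Meier curve and its median with 95% CI, which serve the secondary objective of maintained effect (Section 2.2). The error runs in the favourable direction, and it arises in subjects who needed further AEDs. It also blurs a distinction that the SAP draws itself: treatment retention time (Section 5.2.3 item 4) expressly may include time on concomitant AEDs, and time on monotherapy has no such allowance.

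**Working it through.** The documents state no figure for this endpoint, so there is none to reproduce. The check has three parts.

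**1. Trace the Post-1-Year rule over the possible AED histories**

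| AED added in 1-Year Period | AED added Post-1-Year | Result under Section 5.2.3 item 3 | Consistent with end of monotherapy? |
|---|---|---|---|
| No | No | To last known dose, censored | Yes |
| No | Yes | To that AED, event | Yes |
| Yes | Yes | To the later AED, event | No: too long by the gap between the two AEDs |
| Yes | No | No bullet applies | Undefined |

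In the third row the same subject has an event at the first AED in the 1-Year analysis and at the second in the Post-1-Year analysis, although both measure from the same origin. The event bullet also runs past the end point in its own lead-in, the last dose taken as monotherapy.

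In the fourth row the two last-dose bullets fail, because an AED has been added since the first monotherapy dose. The event bullet fails because none was added in the period. Section 7.6 censors withdrawals without repeating the monotherapy condition.

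**2. One subject in the third row**

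Inputs: 70 days of parent-study monotherapy (Section 6.5 gives 10 weeks; 10 × 7 = 70). Assumed, not from the documents: no gap between studies, first added AED on extension day 120, second on extension day 600.

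- To the first AED: 70 + 120 = 190 days.
- Under the SAP Post-1-Year rule: 70 + 600 = 670 days.
- Overstatement: 670 − 190 = 480 days; ratio 670 / 190 = 3.53.

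**3. Direction and possible size for the curve**

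For a subject in the third row, the SAP time is never earlier than the first-AED time. Censoring a fourth-row subject at last dose would remove an event that had already happened. Both push the curve up.

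To see how far, 20,000 subjects per scenario were simulated and those entering the Post-1-Year Period analysed. All rates are assumptions: hazards for the first and second AED of 0.15, 0.3 or 0.5 per year each (nine combinations), withdrawal 0.2 per year, extension start at day 70, at most 5 years in the extension. Times run from the first monotherapy dose. The equal-hazard scenarios are:

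| Both AED hazards, per year | AED already added at entry | Timed to second AED | No rule | Median, years: first-AED rule | Median: SAP rule, no-rule subjects excluded | Median: SAP rule, no-rule subjects censored at last dose |
|---|---|---|---|---|---|---|
| 0.15 | 14% | 5% | 10% | 4.74 | not reached | not reached |
| 0.3 | 26% | 12% | 15% | 2.48 | 3.20 | 3.64 |
| 0.5 | 39% | 21% | 19% | 1.57 | 2.38 | 2.76 |

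Hand check of the middle row: ln 2 / 0.3 + 70 / 365.25 = 2.31 + 0.19 = 2.50 years, against 2.48 simulated.

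At 3 years with both hazards 0.3, the Kaplan-Meier estimate is 0.43 under the first-AED rule, and 0.54 (excluded) or 0.60 (censored) under the SAP rule. The SAP median was longer, or not reached, in all nine scenarios.

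**The case against.** The strongest reply is that the defect is narrower than it looks.

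- **Not every subject with an earlier AED is mis-timed.** A reader might infer that anyone already on an added AED is timed to a second one and counted as on monotherapy throughout. The text does not support that. Mis-timing needs an addition in each period; a subject who added only in the 1-Year Period has no defined time. This stands.
- **Section 7.6 need not keep that subject event-free.** It first defers to the Section 5.2.3 definition, whose last-dose bullets exclude anyone with an added AED, and for subjects reaching the end it censors only those on eslicarbazepine acetate alone. The withdrawal sentence can be read the other way, so the two sections need reconciling, but it does not settle the matter. It follows that one cannot say each 10% of subjects with an earlier AED lifts the curve by up to 10 percentage points: that ceiling needs all of them to be kept event-free.
- **The 1-Year analysis counts additions in that period on their own dates.** Rule (a) shares the wording, but it misdates an event only if an AED was also added after the first monotherapy dose and before the extension. Section 3.1 admits subjects who discontinued or exited the parent study, so this is possible. Whether and how often it happened depends on parent-study documents not available here.
- **The endpoint is descriptive.** The primary objective is safety and tolerability. This stands and bears on the grade.

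One defence fails: that a programmer would use the first AED anyway. The rule limits the date to an AED started in the named period, so a 1-Year date cannot be used in the Post-1-Year analysis. Nor does the Actual Monotherapy Used subgroup (Section 6.5) help, because time on monotherapy is not among its listed outputs.

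**Conclusion.** The Post-1-Year event rule is wrong as written for subjects who add an AED in each period: it counts time on added AED therapy as monotherapy and biases the Post-1-Year curve and median upward. Subjects who added an AED only in the 1-Year Period have no rule in Section 5.2.3, and Section 7.6 leaves their handling open.

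The direction follows from the text. The size does not: the documents give neither the rate of AED addition nor the number of subjects affected. The 190 and 670 days rest on assumed dates, and the simulated medians on assumed constant hazards; both are illustrations. The documents do not support reading this as a bias in the 1-Year median for AEDs first added during the extension.

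Grade: should-fix, since this is a secondary efficacy endpoint reported descriptively.

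**What to change.** In SAP Sections 5.2.2 item 1, 5.2.3 item 3 and 7.6:

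1. Define the event as the start of the first non-rescue AED on or after the first parent-study monotherapy dose, whether it falls in the parent study, between studies, or in either open-label period. A later AED never resets the date. This also settles which AED counts when two start in one period.
2. Apply the censoring rules, including the one for withdrawals, only to subjects with no such AED.
3. In the Post-1-Year analysis, subjects whose first added AED predates the period keep their event at that earlier date. They are neither timed to a later AED nor censored at last dose.

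Limiting the Post-1-Year analysis to subjects still on monotherapy at Visit 7 would be another choice. With the clock still starting in the parent study, it would guarantee everyone event-free time up to Visit 7 unless delayed entry were also specified. The first-AED definition avoids that.

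The cost is a wording change and one derivation. The current rules already use AED start dates in the extension; the sponsor should confirm that dates for the parent monotherapy phase and any gap between studies are available. The reported Post-1-Year median may become shorter.
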